9.7.1.7 Pharmacokinetic, Pharmacodynamic, Pharmacogenomic, and Other Biomarker Analyses

9.7.1.7.1 PHARMACOKINETIC AND PHARMACODYNAMIC ANALYSES

For the Treatment Phase, summary statistics for serum E6011 concentrations will be calculated by treatment group and evaluation time point. Serum E6011 concentration-time profiles will be plotted.

Population pharmacokinetic analyses will be conducted. Data from other studies will be integrated as necessary. Serum E6011 concentration data will be used to build PK models. The models may be used to explore the relationship between PK and covariates. The relationship between serum E6011 concentrations and biomarkers and/or efficacy will also be investigated through population PK/PD modeling. For population PK analyses, the details will be described in the separately prepared analysis plan and its report, and the results will not be included in the clinical study report.

9.7.1.7.2 PHARMACOGENOMIC, BIOMARKER, AND IMMUNOGENICITY ANALYSES

Pharmacogenomic Analyses

Not applicable.

Biomarker Analyses

For the Treatment Phase, summary statistics for serum RF concentration, serum anti-CCP antibody concentration, and serum MMP-3 concentration, serum TRACP-5b concentration,

serum cytokine concentration, serum LRG1 concentration, serum Ang2 concentration, Vectra™ DA and its component (VCAM-1, EGF, VEGF-A, IL-6, TNF-RI, MMP-1, MMP-3, YKL-40, leptin, resistin, SA and CRP) value, change from baseline and percent change from baseline, by treatment group and evaluation time point, will be calculated. Exploratory investigations of the relationship between efficacy and biomarkers will be conducted. Details and results of analyses of immunocytes such as blood CX3CR1-positive cells will be provided in a separate report, and will not be included in the clinical study report.

Immunogenicity Analyses

All immunogenicity analyses will be performed using the Safety Analysis Set.

The percentage and frequency of occurrences will be calculated for serum anti-E6011 antibodies by treatment group and evaluation time point. If anti-E6011 antibody develops, the frequency and percentage of any anti-E6011 antibody neutralization activity and isotypes will be calculated.

9.7.1.8 Safety Analyses

All safety analyses will be performed on the Safety Analysis Set. For the Treatment Phase, summary statistics for safety data, presented by treatment group, will be calculated on an “as treated” basis (e.g., n, mean, standard deviation, median, minimum, maximum for continuous variables; n and percentage for categorical variables). Safety variables include AEs, clinical laboratory parameters, vital signs, 12-lead ECG results, chest x-ray, neurological findings, and blood CD4-positive cell count. In safety analysis, the date of starting study treatment is treated as Day 1.

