9 INVESTIGATIONAL PLAN

9.1 Overall Study Design and Plan

This study is a multicenter, randomized, double-blind, placebo-controlled, parallel-group comparison study. The following 4 treatment groups are selected for the study: E6011 100 mg, 200 mg, 400 mg, and placebo. In the E6011 100 mg, 200 mg, and placebo groups, subjects will receive the study treatment (100 mg, 200 mg, or placebo, respectively) at Weeks 0, 1, 2, and then every 2 weeks. In the E6011 400 mg group, subjects will receive 400 mg at Weeks 0, 1, 2, 4, 6, 8, 10 and then 200 mg every 2 weeks.

The study consists of Screening, Observation, Treatment, Extension, and Follow-up Phases.

Screening assessments will be performed within 42 days prior to the study treatment, and subjects with the certain eligibility confirmed in the Observation Phase will be allocated to any of the E6011 100 mg, 200 mg, 400 mg, or placebo groups at a 1:2:2:2 ratio through dynamic allocation using the following factors: C-reactive protein (CRP) level at the Screening Phase, disease duration and history of biologics treatment.

In the Treatment Phase (24 weeks), subjects will receive either E6011 or placebo at Weeks 0, 1, 2, and every 2 weeks until Week 22 in a double-blind manner.

Subjects who complete evaluations at Week 24 of the Treatment Phase will enter the Extension Phase. The Extension Phase is up to 104 weeks after the start of the study treatment, and subjects will receive an open-label E6011 200 mg every 2 weeks until Week 102. If the investigator or subinvestigator judges that the response to treatment is insufficient in the Extension Phase, administration of E6011 400 mg every 2 weeks will also be allowed (reduction of the dose back to 200 mg after an increase to 400 mg will also be allowed).

If subjects complete or discontinue the study, a follow-up visit should be conducted 28 days after the completion or discontinuation of the study, and a follow-up visit or telephone interview should be conducted 70 days after the last dosing.

An overview of the study design is presented in Figure 1.

[figure not shown]

Figure 1 Study Design

*: If the investigator or subinvestigator judges that response to treatment is insufficient during the Extension Phase, administration of E6011 400 mg every 2 weeks will also be allowed.

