Since the result from Study 103 suggested the efficacy of E6011 in its 12-week treatment period, the primary endpoint of this study is determined to be ACR20 response rate at Week 12. E6011 is expected to have an inhibitory effect against the structural damage of joints through inhibition of bone absorption in RA. Therefore, modified Total Sharp Score (mTSS), a measure for joint destruction progression, is also evaluated in this study. “The Guideline for the clinical evaluation of antirheumatic drugs” and clinical study data of

similar drugs to E6011 indicate that at least 24 weeks is required for mTSS evaluation; thus, the double-blind part of this study is designed to be 24 weeks.

Subjects who complete the double-blind part for 24 weeks will be able to proceed to the Extension Phase, where E6011 200 mg may be administered every 2 weeks up to Week 104 in an open-label manner. Our target is patients who inadequately respond to MTX, a standard therapeutic agent for RA. Therefore, we consider that the study design where subjects can continue E6011 treatment is useful from the perspective of patient benefit.

Furthermore, if the subjects insufficiently respond to the treatment in the Extension Phase, the design also allows for administration of E6011 400 mg every 2 weeks

The Follow-up Phase was set to be 70 days after the last dose of the study drug, which is approximately 5 times of the longest half-life of E6011 in the previous clinical data.

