9.4 Treatments

9.4.1 Treatments Administered

Treatment Phase: In the E6011 100 mg, 200 mg, or placebo groups, subjects will receive each dose at Weeks 0, 1, 2 and then every 2 weeks up to Week 22 by repeated subcutaneous administration. In the E6011 400 mg group, subjects will receive 400 mg at Weeks 0, 1, 2, 4, 6, 8, 10 and then 200 mg every 2 weeks up to Week 22 by repeated subcutaneous administration.

Extension Phase: Subjects will receive E6011 200 mg every 2 weeks from Week 24 to Week 102 by repeated subcutaneous administration. When subjects

insufficiently respond to the treatment, repeated subcutaneous administration (400 mg of E6011 every 2 weeks) will be allowed.

The study drug contains E6011 50 mg, 100 mg, or placebo in 1 vial (1 mL). In the Treatment Phase, 4 mL will be subcutaneously administered in Weeks 0 to 10, and 2 mL will be subcutaneously administered in Weeks 12 to 22. In the Extension Phase, 2 mL will be subcutaneously administered for the 200 mg dosing and 4 mL will be subcutaneously administered for the 400 mg dosing.

In the 2 mL administration, subjects will receive study drug subcutaneously in 2 separate sites, 1 mL each, from the following sites: right or left upper arm, right or left abdomen, or right or left thigh. In the 4 mL administration, subjects will receive study drug subcutaneously in 4 separate sites, 1 mL each. However, 2 mL of the study drug may be given subcutaneously in 1 site only if the investigator or subinvestigator judges that the study drug can be administered properly.

The dose and administration method for the study drug is described in [Table 1](#).

Study drug will be administered upon completion of all the planned assessments (except for findings on injection sites) on the day of study drug administration. On the first and second administrations of the study drug in both the Treatment and Extension Phases (i.e., Weeks 0, 1, 24, and 26), subjects are required to stay at the site for at least 60 minutes after dosing to confirm its safety before being discharged.

Table 1 Dose and Administration of the Study Drug

Phase	Dose	Dosage Volume	Dosage and Injection Site

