9.4.4 Selection of Doses in the Study

In the Treatment Phase (12 weeks) of Study 103, 21 of 37 subjects (56.8%) experienced adverse events (AEs). AEs occurring in 2 or more subjects were injection site erythema, nasopharyngitis, headache, and oropharyngeal pain. As a dose-dependent increase in the incidence of adverse reactions or occurrence of events to be concerned related to E6011 were not observed in Study 103, we consider that subcutaneous administration of E6011 is generally safe and tolerated in RA subjects at a dose up to 400 mg every 2 weeks. Regarding the efficacy, although Study 103 was an open-label study without a placebo control, the clinical symptoms of RA tended to improve in all of the E6011 100 mg, 200 mg, and 400 mg groups in evaluations up to Week 12.

The relationship between E6011 and its target membrane-bound FKN was investigated based on PK/PD analysis using serum E6011 and total FKN concentrations (sum of free FKN and E6011-FKN complex) in Study 001 and Study 002. Based on the result, the share of membrane-bound FKN for E6011 at Week 12 was estimated to be 98.9% and 99.6% in the E6011 100 mg and 200 mg groups in Study 103, respectively. It is reported that the share of membrane-bound FKN for biologics commercially available as RA drugs and given at clinically recommended dose was estimated to be approximately 99.5% ([Tani K, et al, 2013](#)).

Thus sufficient share of membrane-bound FKN and improvement of clinical symptoms can be expected with E6011 200 mg, and we determined that the administration of 200 mg every 2 weeks is appropriate as a central dose. We also set the dose of 400 mg as a high-dose level, since earlier achievement of sufficient share of membrane-bound FKN and improvement of clinical symptoms may be expected in that dose. However, since 400 mg administration requires 4 subcutaneous administrations (or 2 subcutaneous administrations of 2 mL each), evaluations with 400 mg administrations are limited to 12 weeks (for the primary evaluation period) to reduce the burden on the subjects (particularly those who are given placebo for 24 weeks) and the subjects will receive 200 mg (central dose) subcutaneously in 2 separate sites from Week 12 onward.

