“The guideline for the clinical evaluation of antirheumatic drugs” recommends a Phase 2b study include placebo and 3 doses of active drug. To collect data on the dose response and safety of E6011 with the widest possible dose range, we consider it appropriate to set the following 3 active drug groups: E6011 200 mg as a central dose group; E6011 100 mg as a low-dose group; and E6011 400 mg as initial dose administered until Week 10 and 200 mg after Week 12 as a high-dose group. E6011 100 mg is only set as a dose for evaluation of the dose response and not for evaluation of the efficacy compared with placebo.

In the Extension Phase, subjects will receive 200 mg administrations of E6011 (central dose) every 2 weeks. However, when subjects insufficiently respond to the treatment (E6011 200 mg every 2 weeks), dose escalation will be allowed (E6011 400 mg every 2 weeks).

E6011 is to be administered at Weeks 0, 1, 2, and then every 2 weeks because a loading administration 1 week after the first administration led to the prompt achievement of steady state in PK in Study 103.

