9.7.1.8.2 ADVERSE EVENTS

The AE verbatim descriptions (investigator terms from the CRF) will be classified into standardized medical terminology using the Medical Dictionary for Regulatory Activities (MedDRA). Adverse events will be coded to the MedDRA (Version 19.0 or higher) lower level term (LLT) closest to the verbatim term. The linked MedDRA preferred term (PT) and primary system organ class (SOC) are also captured in the database.

A treatment-emergent adverse event (TEAE) is defined as an AE that emerges during treatment, having been absent at pretreatment (Baseline) or

- Reemerges during treatment, having been present at pretreatment (Baseline) but stopped before treatment, or
- Worsens in severity during treatment relative to the pretreatment state, when the AE is continuous.

Only those AEs that are treatment-emergent will be included in summary tables. All AEs, treatment-emergent or otherwise, will be presented in subject data listings.

The TEAEs will be summarized by treatment group. The incidence of TEAEs will be reported as the number (percentage) of subjects with TEAEs by SOC and PT. A subject will be counted only once within an SOC and PT, even if the subject experienced more than 1 TEAE within a specific SOC and PT. The number (percentage) of subjects with TEAEs will also be summarized by highest CTCAE grade.

The number (percentage) of subjects with TEAEs will also be summarized by relationship to study drug (Yes [related] and No [not related]).

The number (percentage) of subjects with treatment-related TEAEs will be summarized by SOC and PT. Treatment-related TEAEs include those events considered by the investigator to be related to study treatment. The number (percentage) of subjects with treatment-related TEAEs will also be summarized by highest CTCAE grade.

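### Treatment Phase TEAE incidence and extreme-value laboratory shifts are tabulated by arm with no Week 12 cut, so the 400 mg column mixes 400 mg time with 200 mg time

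*Protocol*

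**What the plan says.** Safety and tolerability is one of the two primary objectives (protocol 8.1). Section 9.4.4 gives the reason for the three active groups: "To collect data on the dose response and safety of E6011 with the widest possible dose range".

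The high-dose group does not stay on 400 mg. Under section 9.4.1, "subjects will receive 400 mg at Weeks 0, 1, 2, 4, 6, 8, 10 and then 200 mg every 2 weeks" up to Week 22. Section 9.4.4 explains the step-down by the number of injections: "evaluations with 400 mg administrations are limited to 12 weeks (for the primary evaluation period) to reduce the burden on the subjects".

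The safety text follows the arm, not the dose period. Section 9.7.1.8 states "For the Treatment Phase, summary statistics for safety data, presented by treatment group, will be calculated on an" as-treated basis, and does not say what that means for a scheduled dose change. Section 9.7.1.8.2 adds "The TEAEs will be summarized by treatment group". The measure is the number and percentage of subjects, each counted once per SOC and PT. No split by time or by dose at onset is stated, and no exposure-adjusted rate. Section 9.7.1.8.3 includes shift tables for the highest and lowest value after study drug starts, again with no time limit.

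Other summaries are by visit. These are laboratory values and their shifts from baseline (9.7.1.8.3), vital signs (9.7.1.8.4) and CD4 counts (9.7.1.8.6). The supplied SAP covers the Extension Phase only (SAP section 3). Protocol 9.7 provides for SAPs for the Treatment Phase and for the entire study, and the one for the Treatment Phase is not among the documents.

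**The concern.** The primary efficacy endpoint is read at Week 12, while the high-dose arm has had only 400 mg doses. TEAE incidence and the extreme-value laboratory shifts, as the protocol describes them, are read over 24 weeks, half of which come after the step-down. The column headed 400 mg therefore describes a 400-then-200 mg regimen.

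Weeks 0 to 12 are this study's only randomised, placebo-controlled exposure to 400 mg. In the Extension Phase, 400 mg every 2 weeks is open-label, is given on the investigator's judgement, and can continue up to Week 102. If an excess of adverse events belongs to the 400 mg period, a single 24-week incidence shows it as a smaller ratio. The dose relation for safety, which the dose groups were chosen to show, then looks flatter.

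**Working it through.** **The plan's own figure.** The documents state no power or precision for safety. The only power figures are for ACR20 at Week 12 (protocol 9.7.2): 50 per arm, one-sided 0.0125, chi-square test. They reproduce: 30% against 65% gives 0.911 (stated 91%), and 30% against 60% gives 0.792 (stated 79%). They do not bear on this point.

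**Dose actually given (9.4.1).** The 400 mg arm has 7 doses of 400 mg and 6 of 200 mg: 7 × 400 + 6 × 200 = 4000 mg. The 200 mg arm has 13 × 200 = 2600 mg. The ratio is 4000/2600 = 1.54 over the Treatment Phase, against 2800/1400 = 2 through Week 10.

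**Carry-over.** Section 9.2 sets follow-up at 70 days, "which is approximately 5 times of the longest half-life of E6011 in the previous clinical data". The implied half-life is 70/5 = 14 days. Weeks 12 to 24 are 84 days, or 6 half-lives. If the excess present at Week 12 decays at that rate, its mean over Weeks 12 to 24 is (1 − 2⁻⁶)/(6 ln 2) = 0.984/4.159 = 0.237 of its Week 12 value.

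**Illustration.** These inputs are assumptions, because the documents give no placebo adverse event rate:
- a constant comparator hazard, with 10% incidence over 12 weeks, so S = 0.90;
- a hazard ratio of 2 for the 400 mg arm in Weeks 0 to 12;
- afterwards a hazard ratio of 1 (no carry-over) or an average of 1.237 (carry-over).

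The comparator incidence is 1 − S = 10.0% at 12 weeks and 1 − S² = 19.0% at 24 weeks.

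| Table period | 400 mg arm | Comparator | Risk ratio | Difference |
|---|---|---|---|---|
| Weeks 0–12 | 1 − 0.9² = 19.0% | 10.0% | 1.90 | 9.0 points |
| Weeks 0–24, no carry-over | 1 − 0.9³ = 27.1% | 19.0% | 1.43 | 8.1 points |
| Weeks 0–24, carry-over | 1 − 0.9^3.237 = 28.9% | 19.0% | 1.52 | 9.9 points |

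**Step-down or longer follow-up?** With a hazard ratio of 2 for all 24 weeks, the arm would show 1 − 0.9⁴ = 34.4% against 19.0%, a risk ratio of 1.81. Longer follow-up alone takes the ratio from 1.90 to 1.81. The step-down takes it the rest of the way.

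**Range, without carry-over.**
- Hazard ratio 1.5 to 3 at 10% incidence: the 12-week risk ratio is 1.46 to 2.71, and the 24-week ratio is 1.22 to 1.81.
- Hazard ratio 2 at 2% incidence: the ratio goes from 1.98 to 1.49, and the difference from 2.0 to 1.9 points.
- Hazard ratio 2 at 20% incidence: the ratio goes from 1.80 to 1.36, and the difference from 16.0 to 12.8 points.

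**The case against.** **The regimen comparison is legitimate.** Section 9.4.4 openly defines the high-dose group as 400 mg until Week 10 and 200 mg from Week 12, and a 24-week comparison of randomised regimens answers a real question. All adverse events are also listed by subject. This stands: nothing planned is erroneous. A listing, however, is not a by-arm comparison.

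**Much safety data is already separable.** A reader might infer that all Treatment Phase safety data for 400 mg are diluted. They are not. Laboratory values, vital signs and CD4 counts are shown by visit, and Table 4, note a, puts the Week 12 assessments before that day's dose. Vasculitis markers, CD4 counts, KL-6 and β-D glucan are sampled only twice in the Treatment Phase, at Weeks 12 and 24, so their Week 12 summaries already give the result before the step-down. What remains is TEAE incidence, and extreme values for tests sampled at more visits.

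**The governing SAP is unseen.** A reader might infer that the plan contains no Week 12 cut. The documents show only that the protocol text states none.

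**Incidence is cumulative.** Events from Weeks 0 to 12 stay in the 24-week table, so an absolute excess is largely kept unless events are common. This stands, and it limits the point mainly to ratios.

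**The Study 103 rate is not usable here.** It is tempting to take 56.8% (21 of 37, section 9.4.4) as comparator. With a hazard ratio of 2 and no carry-over, the difference then falls from 24.5 to 10.6 points, a loss of 13.9. With no step-down at all it would still fall to 15.2, so 9.3 of those 13.9 points are a ceiling effect of longer follow-up. The rate also comes from subjects on E6011 in an uncontrolled study.

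**Dilution towards placebo is not established.** The arm stays on active drug after Week 12. The hazard ratio of 1 after step-down fits a comparison with the 200 mg arm; for placebo it would also require 200 mg to add no risk.

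**Conclusion.** The point holds for two outputs as the protocol describes them: TEAE incidence, and the highest/lowest-value laboratory shifts for frequently sampled tests. Both mix 400 mg and 200 mg time under one arm label, and for TEAEs this is the study's only randomised view of 400 mg. It is a gap in the analysis text and a cheap improvement. It is not a contradiction in dosing, and it does not invalidate the 24-week tables.

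Under the stated assumptions, a risk ratio of 1.90 appears as 1.43 to 1.52, while the absolute difference hardly changes. The size depends on the assumed hazard ratio, the assumed comparator rate, and the excess hazard either stopping at Week 12 or fading with the implied half-life. Power is not a useful measure here, because the safety analysis is descriptive and no test is specified. If the Treatment Phase SAP already has a Week 12 cut, citing it closes the point.

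**What to change.** In sections 9.7.1.8.2 and 9.7.1.8.3, or in the Treatment Phase SAP:

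- Add by-arm TEAE tables restricted to onset before the Week 12 dose: all, related, serious, leading to withdrawal, and by highest grade.
- Add the extreme-value laboratory shifts restricted to samples taken before the Week 12 dose, for the tests sampled more often than Weeks 12 and 24.
- State a fixed cut-off day for subjects with no Week 12 dose, for example the scheduled Day 85 in Table 4.
- Keep the 24-week tables as the regimen comparison, and label that column *400 mg to Week 10, then 200 mg*.

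No dose, visit or data collection changes. The cost is one extra set of tables, with fewer events in the 12-week tables and so less precise estimates there.

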9.7.1.8.1 EXTENT OF EXPOSURE

The duration of exposure to study drug will be characterized by treatment group using summary statistics.

9.7.1.8.2 ADVERSE EVENTS

The AE verbatim descriptions (investigator terms from the CRF) will be classified into standardized medical terminology using the Medical Dictionary for Regulatory Activities (MedDRA). Adverse events will be coded to the MedDRA (Version 19.0 or higher) lower level term (LLT) closest to the verbatim term. The linked MedDRA preferred term (PT) and primary system organ class (SOC) are also captured in the database.

A treatment-emergent adverse event (TEAE) is defined as an AE that emerges during treatment, having been absent at pretreatment (Baseline) or

- Reemerges during treatment, having been present at pretreatment (Baseline) but stopped before treatment, or
- Worsens in severity during treatment relative to the pretreatment state, when the AE is continuous.

Only those AEs that are treatment-emergent will be included in summary tables. All AEs, treatment-emergent or otherwise, will be presented in subject data listings.

The TEAEs will be summarized by treatment group. The incidence of TEAEs will be reported as the number (percentage) of subjects with TEAEs by SOC and PT. A subject will be counted only once within an SOC and PT, even if the subject experienced more than 1 TEAE within a specific SOC and PT. The number (percentage) of subjects with TEAEs will also be summarized by highest CTCAE grade.

The number (percentage) of subjects with TEAEs will also be summarized by relationship to study drug (Yes [related] and No [not related]).

The number (percentage) of subjects with treatment-related TEAEs will be summarized by SOC and PT. Treatment-related TEAEs include those events considered by the investigator to be related to study treatment. The number (percentage) of subjects with treatment-related TEAEs will also be summarized by highest CTCAE grade.

